12.3 APPENDIX C: TREATMENT AND MONITORING SCHEDULE: PRE, DURING AND POST THERAPY

	Screening	Baseline ¹	C1 D1	C1 D15	C1 D29	Days 43- 100 (+/- 14)	C2 D1	C2 D15	C2 D2 9	C3 D1 – C5 D1	C6 D1 → 2 years on study	Post- treatment follow-up visit
Serum Beta-HCG ¹⁰	X											
Radiotherapy						X						
GI-6301 (Yeast- Brachyury Vaccine) or placebo ¹¹			X	X	X		X	X	X	X	X ¹¹	
Yeast allergy test ¹²												
Adverse Events		X		X	X		X	X	X	X	X	
Tissue Samples ¹³		X									X	
Concomitant Medications		X		X	X		X	X	X	X	X	
MDASI		X ³								X ³	X ³	
Actigraphy	X	X	X	X	X	X	X	X	X			

¹ Baseline: H & P and laboratory studies should be completed within 16 days of initiating treatment. Baseline radiographic, ECOG performance status, EKG and immunologic studies should be obtained within 28 days of initiating treatment.

² Medical assessments: interim history (since last visit), vital signs, physical examination and ECOG performance status, must be performed within 3 days of each dose

³ Radiologic studies consisting of CT chest/abdomen/pelvis and MRI will be performed within 28 days prior to enrollment, after completion of cycle 2 (on or around C3 D1, and every 3 months (-7 days / +28 days) thereafter. After 1 year of SD, PR, or CR, imaging may be performed approximately every 6 months during year 2, and then yearly thereafter. Imaging can be repeated early at the discretion of the investigator/physician. MDASI assessments will take place along with imaging studies.

⁴ Serum HIV antibody should be completed within 12 weeks of initiating treatment. A positive screening test must be confirmed by detectable virus in the serum by PCR.

⁵ Serum hepatitis B & C antibody should be completed within 12 weeks of initiating treatment. A positive screening test must be confirmed by detectable virus in the serum by PCR.

⁶ Chemistry panel: Na+, K+, Cl-, CO₂, glucose, BUN, creatinine, albumin, calcium, magnesium, phosphorus, alkaline phosphatase, ALT, AST, total bilirubin, TSH, and LDH.

⁷ Blood will be obtained for immunologic assays. Research blood will be drawn at baseline and prior to each dose. 2 SST tubes, 6 green top tubes are required.

⁸ ANA and CD3, 4, 8, 19 subsets will be drawn at baseline and prior to C6 D1.

⁹ For patients with questionable history of yeast allergy, this test is performed at the screening visit to detect if the subject has a hypersensitivity to *Saccharomyces cerevisiae*. **A negative response is required for entry into this trial.**

¹⁰ In females of child-bearing age, beta-HCG to be done within 48 hours prior to day 1.

¹¹ Administered subcutaneously at 4 sites. Dosing will be given as follows: on C1 D1, C1 D15, C1 D29 (all +/- 3 days). Dosing will be interrupted for the duration of radiation and will resume 14-28 days post radiation depending on patient schedule and any time required to recover. Treatment is then resumed on C2 D1, C2 D15, C2 D29 (all +/- 3 days). C3 D1 (28 days (+/- 7 days) after C2 D29) begins monthly (28 day +/- 7 days) dosing for 4 doses (cycles 3, 4, 5, and 6). C6 D1 begins every 3 month (85 days -7/+28 days) dosing, which goes on for at least 2 years. After 2 years on study, doses may be given less frequently (every 6-12 months) based on vaccine supply and patient preference

¹³ Performed in subjects with a questionable history of allergy to yeast

¹³ Baseline tissue sample is preferred. These may be fresh biopsy samples or archived tissue. If archived tissue, at least 10 unstained slides are required. On-study biopsy specimens will be analyzed by immunohistochemistry for evidence of immune response within the tumor. These samples may be obtained at 6 or 12 months or at evidence of tumor response or tumor progression. Biopsy is allowable for research purposes at other times at investigator discretion with patient consent to biopsy.

¹⁴ Post-treatment follow-up labs are not required if the subject prefers to follow-up via phone contact.

[figure not shown]
SPONSOR SIGNATURE

Study Title:	A Randomized, Double-Blind, Phase 2 Trial of GI-6301 (Yeast-Brachury Vaccine) Versus Placebo in Combination with Standard of Care Definitive Radiotherapy in Locally Advanced, Unresectable, Chordoma
Study Number:	QUILT-3.011
Version Date:	14 May 2018

This clinical trial protocol was subject to critical review and has been approved by NantCell.

The following personnel contributed to writing and/or approving this protocol:

Signed:

Date:

5-16-18

[name]
Senior Vice President Adult Medical Affairs, NantKwest Inc.
[name]
[name]
Email: [contact]
[contact]

Abbreviated Title: Ph 2 Yeast-Brachyury Chordoma

NantCell Study number: QUILT-3.011

CC Protocol #: 15-C-0118

OSP#: 1407-1336

Version Date: July 11, 2018

IBC#: RD-15-III-13

Amendment: I

NCT Number: NCT02383498

Title: A Randomized, Double-Blind, Phase 2 Trial of GI-6301 (Yeast-Brachyury Vaccine) Versus Placebo in Combination with Standard of Care Definitive Radiotherapy in Locally Advanced, Unresectable, Chordoma

NCI Principal Investigator:

[name], NOB, CCR, NCI
[name]
[name]
[contact]
Email: [contact]

Sponsor Contact:

[name]
Senior Vice President Adult Medical Affairs
NantKwest Inc.
[name]
[name]
Email: [contact]
[contact]

Investigational Agents:

Drug Name	GI-6301 Vaccine (Yeast-Brachyury)
IND Number	BB-IND # 14895
Sponsor	NantCell, Inc.
Manufacturer/Supplier	GlobeImmune

Commercial Device: wGT3X-BT manufactured by Actigraph. Associate Investigator in the Diabetes, Endocrinology, and Obesity Branch of NIDDK will provide the actigraphy equipment.

PRÉCIS

Background:

- Chordoma is a rare disease, affecting about 3,000 people in the United States, with about 300 new cases diagnosed per year.
- Brachyury is a member of the T-box family of transcription factors, characterized by a highly conserved DNA-binding domain designated as T-domain.
- Brachyury is expressed universally in chordoma cells.
- GI-6301 (Yeast-brachyury vaccine) has demonstrated immunogenicity with a tolerable and acceptable safety profile in a phase 1 trial.
- Brachyury specific T cells can lyse human cancer cells expressing brachyury in an MHC restricted manner.
- There have been indications of clinical benefit in patients with chordoma enrolled on the phase I trial of GI-6301.
 - **1 Partial Response**
 - **1 Mixed Response** in Chordoma patients who received Radiation
 - 6 of 9 patients with progressive disease at enrollment had Stable Disease at Day 85 restaging
- In vitro, chordoma cell lines are killed significantly better by brachyury-specific T cells after radiation exposure using either proton beam or gamma radiation.

Endpoints:

Primary Objective:

- To determine if there is a difference in overall response rate (ORR) defined as complete response (CR) or partial response (PR) by RECIST 1.1 in the irradiated tumor site after up to 24 months among patients with Chordoma who are treated with radiation plus vaccine vs. radiation plus placebo.

Eligibility:

[figure not shown]
- Patients at least 18 years old with advanced unresectable, chordoma who are planning to be treated with definitive radiotherapy to at least one lesion.
- No history of autoimmune disease (with exceptions detailed in section [2.1](#))
- Measurable disease as defined by RECIST 1.1
- Adequate organ function

Design:

- Randomized, double-blind, placebo controlled phase 2 clinical trial of radiation plus placebo vs. radiation plus yeast-brachyury vaccine in patients with chordoma.
- Participants will be randomized on a 1:1 basis to the two arms
- Participants assigned to the placebo arm will be allowed to cross-over at time of confirmed disease progression.

- Participants who have had a response in the irradiated target lesion and then have progression outside of the irradiated site will have the option to receive irradiation or other local intervention to the area of disease outside of the radiation field. Progression will be determined only by the target lesion which had been irradiated. Other lesions will be monitored and intervened upon as clinically necessary. If alternative systemic therapy is required, patients would be taken off study at that point.
- Radiographic progression at the irradiated lesion will be unblinded. Those who did not receive the vaccine will have the option to receive it in combination with radiation to the lesion which is demonstrating disease progression.
- Participants will be evaluated for objective response, and time to progression of the irradiated tumor mass as well as overall survival
- Up to 55 participants will be accrued to the study

Randomization Schema

Primary endpoint: Overall response rate (RECIST 1.1) in the irradiated tumor site(s)

Secondary endpoints:

- Progression free survival (irradiated tumor), PFS (other sites), overall survival
- Patient Report Outcomes

[figure not shown]
Exploratory endpoints:

- Evaluations of response rate and PFS using other criteria
 - (Volumetric, Growth rate kinetics, Choi)
- To evaluate brachyury-specific T cell response pre-, during, and post-treatment.
- To evaluate other parameters of general immune activation detailed in the protocol.
- To evaluate the quantity and quality of tumor infiltrating lymphocytes and other markers of local immune response and inflammation pre- and post-treatment in both groups.
- Daily Activity

Statistical assumption:

- **Goal: improve ORR from 5% to 30%**

Treatment Schema

★ After C7, study agent doses will be given every 3 months (85 days, -7 / +28 days). Restaging scans will be performed at fixed intervals from the time of completion of radiation: 3 months (-7 / +28 days, corresponds to C3D1), 6 months (+/- 4 weeks, corresponds to C6D1), 9 months (+/- 4 weeks, corresponds to C7D1), 12 months (+/- 4 weeks, corresponds to C8D1), 18 months (+/- 8 weeks, C10D1), 24 months (+/- 8 weeks, C12D1), 36 months (+/- 8 weeks, C16D1) and yearly thereafter (+/- 8 weeks). MDASI assessment will take place at baseline and at each restaging timepoint.

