8 STATISTICAL CONSIDERATIONS

The primary objective of the trial is to determine if there is a difference in overall response rate (ORR) defined as complete response (CR) or partial response (PR) by RECIST 1.1 in the irradiated tumor site after up to 24 months among patients with Chordoma who are treated with radiation plus placebo vs. radiation plus vaccine.

Based upon results in the literature³⁵, patients who would be eligible to be randomized on this trial would be expected to have an estimated 5% ORR after up to 24 months if treated in a standard manner with radiation alone. The goal of this study will be to determine if the use of radiation along with vaccine will result in patients having an increased response rate by 24 months which is consistent with 30%.

Following the principles of a phase 2.5 design, to compare these two groups and have 80% power to detect a difference between a 5% and 30% 24 month response rate with a 0.10 one-tailed Fisher's exact test, a total of 25 evaluable subjects per arm (50 total) will need to be randomized over an expected 2 to 3 years, and followed for up to 2 years after randomization.

Patients will be stratified for:

1. Standard fractionation versus hypofractionation radiotherapy dosing
2. Proton versus photon radiation

The vaccine is likely to be very safe, and because the trial is a small randomized phase 2 study, the trial will not require a DSMB to evaluate the findings.

In addition to comparing responses, PFS and OS will be evaluated as secondary endpoints, with Kaplan-Meier curves and a two-tailed log-rank test as the analysis methods. Exploratory evaluations will include response evaluation by other methods, such as Choi and immune-related RECIST criteria (irRC).

It is expected that 20 patients can be accrued onto this trial per year. In order to allow for a very small number of inevaluable patients, the accrual ceiling will be set at 55 patients.

[REDACTED]

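### Could a placebo patient who crosses over to vaccine plus re-irradiation be counted as a placebo responder in the primary ORR?

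*Combined protocol and SAP*

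**What the plan says.** Section 8 (Amendment I; same wording in the other versions in the file) defines the primary endpoint as complete response or "partial response (PR) by RECIST 1.1 in the irradiated tumor site after up to 24 months". The comparison is radiation plus vaccine against radiation plus placebo, and control patients are "expected to have an estimated 5% ORR after up to 24 months if treated in a standard manner with radiation alone".

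The Précis (Design) sets the crossover rules:

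- "Participants assigned to the placebo arm will be allowed to cross-over at time of confirmed disease progression".
- "Progression will be determined only by the target lesion which had been irradiated".
- "Radiographic progression at the irradiated lesion will be unblinded".
- As for treatment after unblinding, patients from the placebo arm "will have the option to receive it in combination with radiation to the lesion which is demonstrating disease progression".

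The same list lets other lesions receive local treatment when clinically needed, and takes a patient off study if another systemic therapy is required. The restaging schedule under the Treatment Schema has scans at 3, 6, 9, 12, 18 and 24 months after radiation, and later.

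The visible text does not say whether a response recorded after crossover counts, for which arm, or against which baseline. It does not say that such a response does count.

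**The concern.** The lesion whose progression opens crossover is the lesion that carries the primary endpoint. A placebo patient could progress at month 6, receive vaccine and further radiation to that lesion, and show a PR at month 18, inside a window that the visible text limits only by calendar time. Read literally, that patient is a placebo-arm responder, although the response followed the experimental treatment.

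Only placebo patients are offered this option, so any contamination runs one way: it raises the placebo rate, shrinks the difference and costs power. The responses would also come after the patient had been unblinded. With 25 per arm and a 5% control rate, about one placebo responder is expected (25 × 0.05 = 1.25), so a single reclassified patient could decide the result.

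**Working it through.** **Inputs from Section 8.** 25 evaluable patients per arm; ORR 5% on placebo and 30% on vaccine; one-sided Fisher's exact test at 0.10; stated power 80%.

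**Step 1: reproduce the plan's figure.** With x placebo and y vaccine responders,

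Power = Σx Σy Bin(x; 25, pP) · Bin(y; 25, pV) · 1[Fisher p(y, x) ≤ 0.10].

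At pP = 0.05 and pV = 0.30 this gives 80.7% (78.8% with 24 per arm). The stated sample size is right on its own inputs.

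**Step 2: how much one patient matters.** The smallest number of vaccine responders that rejects is 4 against 0 on placebo, 5 against 1, 7 against 2 and 8 against 3. For example:

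- 4 v 0: p = C(25,4)/C(50,4) = 12,650/230,300 = 0.055.
- 5 v 1: p = [C(25,5)·25 + C(25,6)]/C(50,6) = (1,328,250 + 177,100)/15,890,700 = 0.095.

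**Step 3: if post-crossover responses were counted.** The documents give neither a crossover rate nor a response rate after crossover. Assume that a share q of placebo patients cross over within 24 months, that a share r of these reach CR or PR at that lesion, and that none of them had responded before. Then pP = 0.05 + q·r, with the vaccine arm held at 30%.

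| q | r | Placebo ORR | Power, 25 per arm |
|---|---|---|---|
| 0 | – | 5% | 80.7% |
| 10% | 10% | 6% | 76.4% |
| 10% | 30% | 8% | 67.7% |
| 20% | 20% | 9% | 63.3% |
| 20% | 30% | 11% | 54.6% |
| 30% | 30% | 14% | 42.4% |

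Adding a fixed number of such responders to the placebo count, without assuming q and r, gives 63.8% for one, 44.6% for two and 28.0% for three.

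**Step 4: direction.** For fixed y, the Fisher p-value rises with x, so extra placebo responders can only make rejection harder. With both arms at 5% the rejection probability is 1.2%, and such counting could only lower it. There is no route to a false positive in the vaccine's favour.

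**Step 5: does the plan count them?** Set the two texts side by side. Section 8 contrasts two treatments and bases its 5% on radiation alone. After crossover under the Précis, a placebo patient has had placebo, radiation, vaccine and radiation again. That patient's later scans describe neither the control treatment nor the population behind the 5%. The reading that fits the plan's own premise classifies the patient on the record before confirmed progression and crossover, as a non-responder if no CR or PR had been seen. Then q·r adds nothing, pP stays at 5%, and power stays at 80.7% with 25 per arm.

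**The case for a change.** The strongest case for a change is that this is the primary endpoint, the ambiguity is one-sided, and one patient can decide the trial. A rule settled after arms are known could be chosen with its effect in view, and writing it down would cost one sentence and no patients. The sensitivity to a single patient stands. So does the observation that the visible Section 8 states no cut-off.

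The rest is weaker.

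- **Absence cannot be established.** Section 8 continues into redacted text, and the sections where response criteria and off-study rules would sit are not public. A rule that cannot be seen is not a missing rule. Response is also tied to RECIST 1.1, whose own conventions cannot be consulted here.
- **The large losses need strong assumptions.** Power of 54.6% or 42.4% takes r = 30%, the full planned vaccine response rate, in a lesion that has already progressed after radiation. The patient must progress, have it confirmed, be treated again and respond, all within 24 months. If the pre-treatment baseline still applies, the lesion must first lose what it gained.
- **Unblinded reading is not shown.** The plan unblinds at progression; the visible text does not say that those who read the scans learn the arm.
- **A broad cut-off has costs.** Ending the window at any first progression call conflicts with the confirmed-progression trigger for crossover. Ending it at any other anticancer treatment would turn patients treated locally elsewhere into non-responders, although the design judges only the irradiated lesion.

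**Conclusion.** No change to the plan follows. The visible text leaves unstated how post-crossover responses are handled, but nothing in it credits them to placebo. The stated comparison and the radiation-alone control rate both point to leaving them out. This is a detail that analysts would fill sensibly: classify placebo patients on what was documented before confirmed progression and crossover, and describe later responses separately. Under that reading the planned 80.7% power holds at 25 per arm.

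Under the opposite reading, power would fall to 76.4% at q = r = 10%, to 63.8% with one added placebo responder, and to 42.4% at q = r = 30%. These rates are assumptions; the documents give none, so the real size is unknown. The error would count against the vaccine. The conclusion rests on the public text, with part of Section 8 and the response-criteria and off-study sections unavailable.

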8 STATISTICAL CONSIDERATIONS

The primary objective of the trial is to determine if there is a difference in overall response rate (ORR) defined as complete response (CR) or partial response (PR) by RECIST 1.1 in the irradiated tumor site after up to 24 months among patients with Chordoma who are treated with radiation plus placebo vs. radiation plus vaccine.

Based upon results in the literature³⁵, patients who would be eligible to be randomized on this trial would be expected to have an estimated 5% ORR after up to 24 months if treated in a standard manner with radiation alone. The goal of this study will be to determine if the use of radiation along with vaccine will result in patients having an increased response rate by 24 months which is consistent with 30%.

Following the principles of a phase 2.5 design, to compare these two groups and have 80% power to detect a difference between a 5% and 30% 24 month response rate with a 0.10 one-tailed Fisher's exact test, a total of 25 evaluable subjects per arm (50 total) will need to be randomized over an expected 2 to 3 years, and followed for up to 2 years after randomization.

Patients will be stratified for:

1. Standard fractionation versus hypofractionation radiotherapy dosing
2. Proton versus photon radiation

The vaccine is likely to be very safe, and because the trial is a small randomized phase 2 study, the trial will not require a DSMB to evaluate the findings.

In addition to comparing responses, PFS and OS will be evaluated as secondary endpoints, with Kaplan-Meier curves and a two-tailed log-rank test as the analysis methods. Exploratory evaluations will include response evaluation by other methods, such as Choi and immune-related RECIST criteria (irRC).

It is expected that 20 patients can be accrued onto this trial per year. In order to allow for a very small number of inevaluable patients, the accrual ceiling will be set at 55 patients.

[REDACTED]

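### At 25 per arm the one-tailed 0.10 Fisher test never has a type I error above 6.0%; Boschloo's exact test lifts power from 80.7% to 84.8% with the same patients and error still below 10%

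*Combined protocol and SAP*

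**What the plan says.** Section 8 (Statistical Considerations), worded alike in all three protocol versions in the file including Amendment I, makes response in the irradiated site by 24 months the primary comparison. Control patients are "expected to have an estimated 5% ORR after up to 24 months if treated in a standard manner with radiation alone". The design is meant to "have 80% power to detect a difference between a 5% and 30% 24 month response rate", and the test and sample size are given as "with a 0.10 one-tailed Fisher's exact test, a total of 25 evaluable subjects per arm (50 total"). The précis sets the allocation: "Participants will be randomized on a 1:1 basis to the two arms". For losses, Section 8 says "In order to allow for a very small number of inevaluable patients, the accrual ceiling will be set at 55 patients".

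The readable text does not give the type I error that the Fisher test actually attains at this size, and it names no alternative exact test. It lists two stratification factors (fractionation and beam type) but describes no stratified primary test. The text that follows Section 8 is blacked out.

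**The concern.** Fisher's test computes its p-value given the total number of responders. When that total is small, only a few p-values are possible, and the largest one at or below 0.10 is often far below it. Averaged over the totals that can occur, the true false-positive rate falls well short of 0.10. The sponsor has accepted a 10% risk of a false positive in return for a small trial, but the test does not use that allowance.

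The unused error costs power. The précis puts new US cases at about 300 a year and Section 8 expects to accrue 20 patients a year, so patients cannot easily be added. Some results that a valid exact test at the 10% level would call positive would be declared negative.

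**Working it through.** **Inputs (Section 8 and précis).** n = 25 evaluable per arm, 1:1; one-sided α = 0.10; response rates 5% (placebo) and 30% (vaccine).

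**Method.** Let x be placebo responders and y vaccine responders. Every one of the 26 × 26 tables was enumerated.

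- Probability of a table: Bin(x; 25, p₀) × Bin(y; 25, p₁).
- One-sided Fisher p-value: P(Y ≥ y | x + y responders in total), from the hypergeometric distribution with 25 of 50 patients in the vaccine arm.
- Power: sum of the table probabilities over the rejection region at p₀ = 0.05, p₁ = 0.30.
- Size: the same sum at p₀ = p₁ = p. Maximum size is the largest value over a fine grid of p from 0 to 1.
- Boschloo region: order the tables by Fisher p-value and take the largest region whose maximum size is at or below 0.10.

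**Step 1: the plan's own figure.** Rejecting when Fisher p ≤ 0.10 gives power 80.69% at 25 per arm and 78.84% at 24 per arm. The stated 80% at 25 per arm is reproduced.

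**Step 2: actual error of the Fisher test.** Size is 1.21% at p = 0.05, 3.96% at 0.10 and 5.71% at 0.20. The maximum is 5.95%, at p = 0.50.

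**Step 3: Boschloo at the same n.** The cut-off on the Fisher p-value is 0.1281. The next table in the ordering (p = 0.1289) would take the maximum size to 10.13%, so the region cannot be enlarged.

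| 25 per arm | Fisher | Boschloo |
|---|---|---|
| Power, 5% v 30% | 80.7% | 84.8% |
| Maximum size | 5.95% | 9.34% |
| Size at common 5% | 1.2% | 3.8% |
| Power, 4.5% v 27% | 75.4% | 80.5% |
| Power, 5% v 25% | 66.9% | 72.9% |

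The gain at the planned rates is 84.81 − 80.69 = 4.12 points. The type II error falls from 19.3% to 15.2%, about a fifth.

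**Step 4: which results change.**

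| Placebo responders | Fewest vaccine responders to reject: Fisher | Boschloo |
|---|---|---|
| 0 | 4 | 3 |
| 1 | 5 | 5 |
| 2 | 7 | 6 |
| 3 | 8 | 8 |
| 4 | 9 | 9 |

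Two results change at these counts:

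- 3 v 0: Fisher p = C(25,3)/C(50,3) = 2,300/19,600 = 0.117.
- 6 v 2: Fisher p = [C(25,6)·C(25,2) + C(25,7)·C(25,1) + C(25,8)]/C(50,8) = 66,229,075/536,878,650 = 0.123.

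Their contributions to power at 5% v 30%:

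- 6 v 2: 0.2305 × 0.1472 = 3.39 points.
- 3 v 0: 0.2774 × 0.0243 = 0.67 points.

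Together they make 4.06 of the 4.12 points; tables with five or more placebo responders supply the rest.

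Their contributions to size at a common 5%:

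- 3 v 0: 0.2774 × 0.0930 = 2.58 points.
- 6 v 2: 0.2305 × 0.0010 = 0.02 points.

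That accounts for the rise from 1.21% to 3.82%.

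**Step 5: worth in patients, and other arm sizes.** Boschloo with 22 per arm already gives 81.5%, so the gain is worth about 3 patients per arm, or 6 in total. At 20 patients a year that is 6/20 × 12 = 3.6 months of accrual. With other evaluable numbers the cut-off is recalculated:

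| Vaccine / placebo | Fisher power | Boschloo power | Boschloo maximum size |
|---|---|---|---|
| 24 / 24 | 78.8% | 84.9% | 9.7% |
| 26 / 24 | 78.8% | 84.5% | 9.6% |
| 24 / 26 | 80.9% | 84.0% | 9.6% |
| 25 / 24 | 77.4% | 85.6% | 9.8% |

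Losing one evaluable patient per arm, or ending with 26 vaccine and 24 placebo patients, takes Fisher below its stated 80%. Boschloo stays at 84% or more in every row.

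**The case against.** The best defence is that nothing in the plan is wrong. The sample size was derived for Fisher's test, so its strictness is already paid for in n, and the promised 80% is met. Nominal α is a ceiling, and attained size below it is not a validity fault. Choosing conditional over unconditional inference is a respectable position. All of that stands, which is why this is an efficiency point.

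The change also has a cost: at the planning rate the false-positive probability roughly triples, from 1.2% to 3.8%. Nearly all of that rise comes from 3 v 0, a 12% vaccine response rate that is far from the targeted 30%. This should be stated openly. It remains well inside the 10% the sponsor chose, and most of the power gain comes from 6 v 2, a 24% vaccine response rate.

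Timing matters too. The current text is Amendment I of July 2018, and the précis provides for unblinding when the irradiated lesion progresses. A switch to a test that rejects strictly more results would look data-driven unless it is fixed before comparative response data are seen. That is a condition on the fix, not a reason against it.

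Finally, the cut-off of 0.128 and the 84.8% belong to exactly 25 v 25. True, but the test recalibrates to the actual arm sizes, and the gain was between 3 and 8 points in every split shown above. The comparison here is unstratified, like the test the readable text plans. Whether the blacked-out text adds analysis detail cannot be known.

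**Conclusion.** The point holds as an improvement to a correctly sized design. At 25 per arm the planned test has a true one-sided error of 1.2% at the planned control rate and never above 6.0%, against a nominal 10%. Boschloo's test raises power from 80.7% to 84.8%, keeps the error at or below 9.3% for every common response rate, and loses no result that Fisher would call positive. It also gives the design a margin against a lost patient or an uneven split that the Fisher test lacks.

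These figures assume independent binomial responses, an unstratified comparison, true rates of 5% and 30%, and 25 evaluable patients in each arm. The size of the gain changes with those inputs. The guarantee that error stays at or below 10% does not depend on the response rates, provided the cut-off is computed for the actual arm sizes.

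**What to change.** In Section 8, name Boschloo's one-sided exact unconditional test at 0.10 as the primary test of response rate, with the p-value computed for the numbers actually evaluable in each arm, and report the one-sided Fisher p-value beside it. Keep 25 evaluable per arm and restate power as about 85% for 5% v 30%. State the attained error: at most 9.3% overall, and 3.8% at a common 5% rate. Make the change by documented amendment before any comparative response data are seen; if that point has passed, keep Fisher as primary and report Boschloo as supportive only.

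The cost is an amendment to one sentence, with no extra patients, visits or follow-up, and the test is available in standard software. The price is a less familiar test and an actual false-positive rate that is higher than Fisher's but within the 10% already accepted.

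### The PFS and OS log-rank test in Section 8 is named without the two stratification factors; stratifying it is a cheap, optional improvement for secondary endpoints

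*Combined protocol and SAP*

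**What the plan says.** Section 8 (Statistical Considerations) reads the same on this point in all three protocol versions in the file. It states "Patients will be stratified for" two factors: "Standard fractionation versus hypofractionation radiotherapy dosing" and "Proton versus photon radiation". I read this as stratified randomization, which the text implies but does not spell out. Two paragraphs later it says that "PFS and OS will be evaluated as secondary endpoints, with Kaplan-Meier curves and a two-tailed log-rank test as the analysis methods". The test carries no qualifier, and the factors are not mentioned again in the visible text.

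The précis lists the secondary endpoints as "Progression free survival (irradiated tumor), PFS (other sites), overall survival", so more than one PFS comparison is meant. Its Design section adds that "Participants assigned to the placebo arm will be allowed to cross-over at time of confirmed disease progression", which bears on OS. Section 8 has patients "followed for up to 2 years after randomization", while the Treatment Schema schedules scans at 36 months and yearly after that.

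The only comparison that is sized is the primary one: 25 evaluable patients per arm, 5% versus 30% response, one-tailed Fisher's exact test at 0.10, 80% power. No event count, hazard ratio or significance level is given for PFS or OS.

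**The concern.** When allocation is balanced within prognostic groups, the arms are more alike than chance alone would make them. An unstratified log-rank test computes its variance as if that balance had not been imposed. It therefore overstates the variance, rejects a true null less often than its nominal level, and gives up power. A test stratified by the same factors recovers this.

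What is at stake is modest: some power for PFS in a trial with few events. There is also a benefit that does not depend on prognosis. Naming one test in advance leaves no later choice between a stratified and an unstratified p-value.

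**Working it through.** **1. The plan's own figure.** Exact power of the one-tailed Fisher test is the sum over x and y of Bin(x; n, 0.05) × Bin(y; n, 0.30), taken over tables with P(Y ≥ y | x + y) ≤ 0.10. At n = 24 per arm this is 78.8%; at n = 25 it is 80.7%. So 25 is the smallest size reaching 80%, and the stated figure reproduces.

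**2. The two log-rank tests.** At each event j, let r be the number at risk and r1 the number at risk on vaccine. Then U = Σ(d1j − dj·r1j/rj), V = Σ dj·(r1j/rj)(1 − r1j/rj), and Z = U/√V. The stratified version forms U and V within each of the 2 × 2 = 4 cells and uses Z = ΣU_s/√ΣV_s.

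**3. Inputs.** From the documents: 50 patients, 1:1 allocation, two binary factors, a two-tailed test. Assumed, because the visible text does not give them: two-sided 5%; permuted blocks of 4 within cells; each factor 40% or 25% prevalent with the same prognostic hazard ratio (HR); exponential times; PFS control median 18 months; treatment HR 0.45. Follow-up is either censoring spread over 24 to 54 months (about 31 PFS events) or a 24-month cap (about 24 events). There were 20,000 simulated trials per scenario, with a Monte Carlo standard error of at most 0.35 points.

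**4. Size with no treatment effect.** The unstratified test rejects in 3.9 to 4.3% of trials at prognostic HR 2 per factor and in 2.4 to 3.1% at HR 3. A separate simulation with 50% prevalence and a 24-month median gave 5.3%, 4.8%, 3.9% and 2.6% at HR 1, 1.5, 2 and 3, against 5.2%, 5.4%, 5.4% and 5.6% stratified. Another, at 40% prevalence, gave 3.8% and 2.3% at HR 2 and 3, against 4.9% and 5.7% stratified. The stratified test thus tends to run slightly above 5% in cells this small, which accounts for a small part of its power advantage.

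**5. PFS power (%), stratified minus unstratified.**

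| Prevalence, follow-up | HR 1 | HR 1.5 | HR 2 | HR 3 |
|---|---|---|---|---|
| 40%, 24–54 months | 56.6 − 59.8 = −3.2 | 56.2 − 57.1 = −0.9 | 54.6 − 50.8 = +3.8 | 54.0 − 41.2 = +12.8 |
| 25%, 24–54 months | 57.3 − 60.1 = −2.8 | 56.0 − 57.6 = −1.6 | 54.7 − 53.0 = +1.7 | 53.4 − 43.4 = +10.0 |
| 40%, 24-month cap | 47.2 − 48.4 = −1.2 | 46.9 − 46.8 = +0.1 | 47.2 − 43.4 = +3.8 | 46.3 − 35.2 = +11.1 |
| 25%, 24-month cap | 47.0 − 48.2 = −1.2 | 46.6 − 47.2 = −0.6 | 45.9 − 43.8 = +2.1 | 45.4 − 37.0 = +8.4 |

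The gain is therefore 1.7 to 3.8 points at HR 2 and 8.4 to 12.8 at HR 3. The loss at HR 1 is 1.2 to 3.2 here, and up to about 4 in the separate 40% simulation.

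**6. Simple randomization.** The unstratified size is 5.2 to 5.3%. At HR 2 (40% prevalence, 24 to 54 months), power is 51.0% unstratified and 52.0% stratified. The effect comes from balance within strata.

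**7. OS.** With an assumed 48-month control median, treatment HR 0.45 and no crossover, there are 11 to 18 events and unstratified power is 22 to 34%. If 80% of progressing placebo patients cross over and their hazard is then multiplied by 0.45, there are 10 to 16 events and power is 12 to 18%. Gains for OS were computed only for a test that drops to one factor when a cell has fewer than 6 patients. With crossover they were 0.3 to 1.1 points at HR 2 and 1.1 to 3.5 at HR 3.

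**The case against.** The strongest reply is that nothing is wrong. A log-rank test named without a qualifier is ordinarily the unstratified one. The primary Fisher test is unstratified too, so the plan is coherent: balance by design, then simple tests. The chosen test is valid, and these are unpowered secondary endpoints in a 50-patient phase 2 trial. The benefit rests on prevalence, prognostic strength and allocation method, none of which the visible text gives. The sign of the effect depends on them, and gains of 8 points or more need HR 3 for both factors, a 3 × 3 = 9-fold range of hazard across cells.

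All of this stands, and it is why the point is optional. It does not remove the point. The plan already chose to stratify on these factors, and using them in the analysis takes only wording.

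A reader might infer that an unstratified test after stratified randomization inflates type I error. The calculation shows the opposite: with balanced allocation it falls below 5%. A reader might also infer that the primary analysis is at risk, but its power reproduces and nothing here touches it. Nor do the documents support saying that the trial will lose power, since nowhere in the visible text are the factors said to be prognostic. The absence of a stated allocation method is not a fault either: text after Section 8 is redacted.

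**Conclusion.** The point holds as a low-priority improvement to the secondary analyses. As written, the PFS and OS log-rank test is unstratified although patients are stratified by two factors. If allocation is balanced within strata and both factors are prognostic, the test is conservative: size about 4% at HR 2 per factor and 2 to 3% at HR 3. The PFS power given up is then about 2 to 4 points and 8 to 13 points respectively. Near HR 1.5 the two tests are about equal, and at HR 1 the unstratified test is slightly better.

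These sizes rest on the assumed treatment effect, median, prevalences and block size. With a weaker assumed PFS treatment HR of 0.65, power is at most 25%, so the choice of test matters less. For OS the benefit is small because events are few and crossover dilutes the comparison. The conclusion concerns the visible text only; if a redacted part already names a stratified test, confirming that is enough.

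**What to change.** In Section 8, state that the log-rank tests for OS and for each PFS endpoint, and any hazard ratio reported with them, are stratified by fractionation and by proton versus photon as recorded at randomization. That has to mean planned radiotherapy, because Appendix C places radiotherapy at Days 43–100, after the three cycle 1 doses. Report the unstratified log-rank test as a sensitivity analysis. Leave the primary one-tailed Fisher's exact test as it is.

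The cost is a sentence or two, fixed before unblinding; no sample size, visit or primary result changes. The statistical price is about 1 to 4 points of PFS power if neither factor turns out to be prognostic.
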